- 2) 4-Dimensional CT Simulation Scan
- 3) ITV based “standard” SABR planning with 5mm PTV Expansion margins
- 4) Image guided “Standard” SABR (54Gy/3#)
- 5) Quality Assurance measurements
- 6) Quality of Life and Toxicity Assessments

Phase II (n=26)

Adults ≥ 18 years of age
T1N0M0 or T2N0M0 (<4cm) NSCLC; or
A single Metastatic Lung Tumor < 4cm
ECOG performance status 0 to 2
Surgically inoperable
Non-Oxygen dependent at baseline

Calypso Guided Stereotactic Ablative Radiotherapy:

- 1) Endobronchial Calypso Beacon Placement
- 2) 4-Dimensional CT Simulation Scan
- 3) ITV-free and 2mm PTV margin SABR planning
- 4) Respiratory gated Calypso guided SABR (54Gy/3#)
- 5) Quality of Life and Toxicity Assessments
- 6) Radiotherapy dosimetry planning studies

Planned Sample Size: Phase I (n=2); phase II (n=26)

2.0 Background:

Stereotactic Ablative Body Radiotherapy (SABR)

Stereotactic Ablative Body Radiosurgery (SABR) is a modern radiotherapy technique which consists of the delivery of tumoricidal (ablative) doses of radiation to a tumor target inside the body. In contrast to conventional radiotherapy which delivers the total dose to the tumor over six to seven weeks with small daily doses of radiotherapy (2 Gy per fraction for 30 to 33 fractions), SABR is delivered using much larger ablative doses of radiotherapy per fraction (ranging from 8 to 34 Gy per fraction) allowing for the total dose to be delivered in a small number of fractions (1 to 5 fractions). With larger doses per fraction, and delivery of radiotherapy over a shorter period of time, SABR affords a larger biological effective dose of radiotherapy when compared to conventional fractionated radiotherapy. In general, most SABR dose regimens have biological effective doses in excess of 100Gy delivered with conventional fractionation.

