- 4) ECOG performance status of 0 to 2.
- 5) Minimum life expectancy of 6 months.
- 6) Deemed fit to undergo bronchoscopy by their participating thoracic surgeon
- 7) Deemed fit to undergo SABR by their participating Radiation Oncologist.
- 8) Respiratory function (a patient must satisfy both “a” and “b” below):
 - a. Minimum FEV1 of 0.8 liters
 - b. Minimum DLCO of 35% predicted.
- 9) Able to provide written informed consent and understand verbal instructions necessary for radiotherapy treatments.

Exclusion Criteria:

- 1) Tumors located < 1 cm from the chest wall based on CT imaging.
- 2) Tumors located ≤ 2 cm from the proximal bronchial tree (see figure 7)
- 3) Patients who require supplemental oxygen at rest.
- 4) Patients who are unable to lie flat or still for a minimum of 30 minutes.
- 5) ECOG performance status 3 or 4.
- 6) Evidence of uncontrolled extra-thoracic metastatic disease (based on imaging or clinical findings).
- 7) Proven or suspected intrathoracic lymph node involvement.
- 8) Prior SABR to the target tumor.
- 9) Prior history of idiopathic pulmonary fibrosis, interstitial lung disease, or active collagen vascular disease (systemic lupus erythematosus, Rheumatoid arthritis, or Scleroderma)
- 10) Pregnancy.
- 11) Active pulmonary infection
- 12) Known hypersensitivity to nickel titanium (Nitinol)
- 13) Known Bronchiectasis of the small airways nearest to the tumor

Figure 7: The proximal bronchial tree (tumours within this region are ineligible for trial participation).**6.0 Study Objectives:****Phase I:**

- 1) To allow for members of the interdisciplinary care team (Thoracic surgeons, Radiation Oncology, Radiation Therapists, and Medical Physicists) to familiarize themselves with the clinical use of implanted endobronchial tumor tracking beacons and carry out quality assurance assessments in preparation for the subsequent phase II component of the study.
- 2) To quantify the presence (if any) of beacon migration (inter-beacon distance) at different time points in a patient's care path (time of implantation, CT simulation scan, and days of SABR treatment).
- 3) To assess the quality of life of patients having Calypso placement (EORTC QLQ - LC13 questionnaire)
- 4) To assess acute toxicity of beacon implantation using the Common Terminology for Criteria for Adverse Events (CTCAE version 4.0)

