- 5) To quantify the potential benefit of continuous monitoring of tumor location using Calypso by comparing it to traditional imaging-based setup.

Phase II:

- 1) To quantitatively assess the differences in irradiated treatment volumes and radiotherapy dose volume metrics for the PTV and healthy thoracic organs at risk between Calypso™ guided respiratory gated SABR and the traditional ITV based radiotherapy.
- 2) To serially quantify the acute and late toxicity of patients undergoing Calypso™ guided SABR using the Common Terminology Criteria for Adverse Events (CTCAE) Version 4.0
- 3) To serially quantify the self-reported quality of life of patients undergoing Calypso Guided SABR using the EORTC QLQ - LC13 questionnaire
- 4) To serially biobank blood and urine samples for patients undergoing radical SABR of lung tumors to allow for the future development of novel prognostic and predictive biomarkers for patients undergoing SABR.
- 5) To serially quantify changes to pulmonary function following SABR treatment

- 6) To demonstrate the benefit of Calypso treatments in reducing patient-specific component of PTV margins

Study Hypotheses:

Phase I: Calypso beacon placement will be safe and well tolerated and will function within their specified tolerances with minimal (sub-millimeter) inter-beacon migration.

Phase II: The Median Planning Target Volume (PTV) of Calypso guided respiratory gated SABR will be 40% smaller than the median PTV volume of standard ITV based SABR treatment with standard PTV margins. Furthermore, thoracic organs at risk will receive significantly less radiotherapy dose when compared to the standard SABR treatment.

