| | none | minor | none | minor | none | minor | none | minor | |
| 2.0 | <1.2 | 1.2-1.4 | <3.9 | 3.9-4.1 | <28.1 | 28.1-30.1 | <10 | 0-15 | 1.8 |
| 2.5 | <1.2 | 1.2-1.4 | <3.9 | 3.9-4.1 | <28.1 | 28.1-30.1 | <10 | 10-15 | 3.8 |
| 3.0 | <1.2 | 1.2-1.4 | <3.9 | 3.9-4.1 | <28.1 | 28.1-30.1 | <10 | 10-15 | 7.4 |
| 3.5 | <1.2 | 1.2-1.4 | <3.9 | 3.9-4.1 | <28.1 | 28.1-30.1 | <10 | 10-15 | 13.2 |
| 4.0 | <1.2 | 1.2-1.4 | <3.8 | 3.8-4.0 | <30.4 | 30.4-32.4 | <10 | 10-15 | 21.9 |
| 4.5 | <1.2 | 1.2-1.4 | <3.7 | 3.7-3.9 | <32.7 | 32.7-34.7 | <10 | 10-15 | 33.8 |
| 5.0 | <1.2 | 1.2-1.4 | <3.6 | 3.6-3.8 | <35.1 | 35.1-37.1 | <10 | 10-15 | 49.6 |
| 5.5 | <1.2 | 1.2-1.4 | <3.5 | 3.5-3.7 | <37.4 | 37.4-41.7 | <10 | 10-15 | 69.9 |
| 6.0 | <1.2 | 1.2-1.4 | <3.3 | 3.3-3.5 | <39.7 | 39.7-41.7 | <10 | 10-15 | 95.1 |
| 6.5 | <1.2 | 1.2-1.4 | <3.1 | 3.1-3.3 | <42.0 | 42.0-44.0 | <10 | 10-15 | 125.8 |
| 7.0 | <1.2 | 1.2-1.4 | <2.9 | 2.9-3.1 | <44.3 | 44.3-46.3 | <10 | 10-15 | 162.6 |

11.0 Potential Adverse Reactions:

The adverse effects associated with the use of the Calypso transponder beacons are similar in profile to other bronchoscopic procedures such as bronchoscopic biopsies or the implantation of inert gold seed fiducial markers.

Pneumothorax: The most commonly encountered adverse effect of fiducial marker placement is pneumothorax which has a risk of between 2 to 5 percent^{27,28} with the majority of these treated either conservatively or with a pigtail catheter for a day or two²⁴ after the procedure.

COPD Exacerbations: Exacerbations of emphysema or chronic obstructive pulmonary disorder (COPD) have been reported with a risk of up to 11 percent²⁹ in one small case series of 9 patients who had non-calypso beacons implanted. However, several much larger case series reported no COPD exacerbations^{24,27,28} whatsoever.

Beacon Migration: Beacon migration has been reported at a rate of 1%²⁴ using anchored calypso beacons which can lead to the expectoration of the migrated beacon.

Infection: There is a 1% risk of pulmonary infection in the tissue in close proximity to an anchored Calypso beacon²⁴.

Minor Bleeding: There is a small risk of minor local bleeding in the airway implanted with the transponder beacon with a risk similar to other bronchoscopic based procedures, however no pulmonary hemorrhages were reported in the case series using the anchored Calypso lung beacon²⁴.

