|--|---------------------------|
| Age | Mean & Standard Deviation |
| Gender | Percentage |
| Comorbidity (Charlson Index) | Mean & Standard Deviation |
| Smoking History Category (Current smoker, previous smoker, never smoker) | Percentage |
| Smoking Pack-Year History | Mean & Standard Deviation |
| FEV1 (Liters) | Mean & Standard Deviation |
| Diffusion Capacity (%) | Mean & Standard Deviation |
| 6 Minute Walk Test (% of expected distance) | Mean & Standard Deviation |
| Tumor Factors | |
| T-stage (T1, T2) | Percentage |
| Tumor size (cm ³) | Mean & Standard Deviation |
| Tumor location (by lobe) | Percentage |
| Tumor Histology | Percentage |
| Treatment Factors | |
| GTV (cm ³) | Mean & Standard Deviation |
| PTV (cm ³) | Mean & Standard Deviation |
| Maximal observer tumor motion (cm) | Mean & Standard Deviation |
| Radiotherapy Dose Prescription (cGy) | Percentage |
| Radiotherapy Delivery Time Per Fraction | Mean & Standard Deviation |

Study Power:

Power calculations were conducted using the STATA 12.0 statistical software package (College station, Texas). Zhao *et al.*²² carried out dosimetric analyses of lung tumors undergoing SABR lung treatments with similar characteristics (T1-T2N0 NSCLC) to those which would be eligible for this study and found a median PTV volume of 62.9 cm³ (sd 43.6 cm³). Presuming similar sized tumor volumes as Zhao *et al.*, A sample size of 28 patients would yield a power of 0.92 to detect a 40% reduction in the mean PTV volume between standard ITV based SABR treatment as compared to gated calypso guided SABR, with an alpha value of 0.05 and using a 1-sided test for statistical significance.

Endpoints:

Percentage Change in PTV: For each participating patient, the PTV volumes will be calculated on the same 4DCT for standard ITV-based SABR treatment as well as the Calypso guided SABR treatment. The comparison of the PTV volumes will be calculated as follows:

$$\% \text{ change in PTV} = (\text{PTV}_{\text{standard SABR}} - \text{PTV}_{\text{Calypso Guided SABR}}) / (\text{PTV}_{\text{standard SABR}}) \times 100$$

This metric will be reported as a mean for the cohort with SD

Quality of Life Data: The mean EORTC QLQ – LC13 plus standard deviation will be tabulated in descriptive format for each evaluation time point.

Acute and Late Toxicity: The maximum grade of observed toxicity during treatment and follow-up will be tabulated in a descriptive format by adverse effect.

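### Toxicity is summarised as one maximum grade per adverse effect over up to three years, with no implant-period window for the 28 implanted patients and no split into acute and late

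*Combined protocol and SAP*

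**What the plan says.** The numbers are in section 1.0: "Planned Sample Size: Phase I (n=2); phase II (n=26". The phase I and phase II treatment lists there both begin with "1) Endobronchial Calypso Beacon Placement", so every patient has the bronchoscopic implant.

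Section 6.0 names implant toxicity only under phase I, objective 4: "To assess acute toxicity of beacon implantation using the Common Terminology for Criteria for Adverse Events (CTCAE version 4.0". Phase II objective 2 reads "To serially quantify the acute and late toxicity of patients undergoing Calypso™ guided SABR" and does not name implantation. The hypothesis that "Calypso beacon placement will be safe and well tolerated" is also labelled phase I. Section 7.0 has a single secondary endpoint for acute and late toxicity, not divided by phase or by cause.

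The only planned summary is in section 13.0: "The maximum grade of observed toxicity during treatment and follow-up will be tabulated in a descriptive format by adverse effect". It gives no time window, attribution, denominator or interval. The quality-of-life paragraph just before it tabulates results at each evaluation time point.

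The section 12.0 schedule has CTCAE grading at baseline, 4DCT simulation, each fraction, and 2, 6, 12, 18, 24 and 36 months, with no restriction by phase. The 4DCT may follow the implant by up to 4 weeks, and the first fraction may follow the 4DCT by up to 14 days.

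**The concern.** The implant is a separate invasive procedure with its own listed risks (section 11.0), given before any radiation. A maximum taken over the whole course discards the date of the event. For terms that only one procedure produces, little is lost. For shared terms, an implant-period event and a radiation event compete for one cell, and only the higher grade survives.

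Two things are at stake. The first is the tolerability statement for beacon placement. As the objectives stand, it is formally assigned to two patients, while 26 more have the same procedure and the same pre-SABR assessments. The second is the use of the data. Section 1.0 says that toxicity is collected to help size a later randomised trial, and for that purpose implant-period, acute and late rates are more useful apart than merged. Patients with poor pulmonary function, whom the background section describes as typical for SABR, are those in whom the shared respiratory terms matter most.

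**Working it through.** **Plan's own figure.** The plan states no precision or sample size for toxicity. Its one calculated figure, power 0.92, concerns PTV. It reproduces under a one-sample normal approximation: 0.40 × 62.9 = 25.16; 43.6/√28 = 8.24; Φ(25.16/8.24 − 1.645) = 0.9205. It has no bearing on this point.

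**Inputs.** Patients: 2 in phase I, 26 in phase II, total 2 + 26 = 28 (section 1.0). Longest gap from implant to first fraction: 28 + 14 = 42 days (section 12.0 notes). Pneumothorax risk of marker placement: 2% to 5% (section 11.0).

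**Step 1: what the maximum keeps.** Take one shared term, with invented grades for three patients:

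- Grade 2 after implant, grade 3 at 12 months: table shows 3.
- Grade 2 after implant, grade 1 at 12 months: table shows 2.
- Nothing after implant, grade 2 at 12 months: table shows 2.

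The implant event of the first patient is overwritten. The second and third patients look identical. That radiation as well as the implant can cause cough, dyspnea, hypoxia, bleeding or infection is a clinical assumption; the protocol gives no list of shared terms.

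**Step 2: acute against late.** Objective 2 and the section 7.0 endpoint both name acute and late toxicity, and objective 2 asks for serial quantification. A single maximum from treatment to 3 years is neither serial nor split.

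**Step 3: what each denominator can support.** With zero events, the two-sided exact 95% upper limit is 1 − 0.025^(1/n):

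- n = 2: 1 − 0.025^(1/2) = 0.842, so 0 to 84.2%.
- n = 28: 1 − 0.025^(1/28) = 0.123, so 0 to 12.3%.

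With one event in 28, the exact interval is 0.1% to 18.3%; with two, 0.9% to 23.5%.

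**Step 4: chance of seeing a listed event.** The chance of at least one pneumothorax is 1 − (1 − p)^n:

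- n = 2: 1 − 0.98² = 4.0% to 1 − 0.95² = 9.8%.
- n = 28: 1 − 0.98^28 = 43% to 1 − 0.95^28 = 76%.

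This shows how little two patients can say about tolerability. It is not the gain from the fix, because pneumothorax in any of the 28 is already tabulated.

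**Step 5: are the data there?** Baseline and 4DCT grades bracket the implant with no SABR between them, in every patient. Change from baseline to 4DCT can therefore be summarised without a new visit.

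**The case against.** The strongest reply is that little is lost. The table is by adverse effect, and Appendix II lists pneumothorax, pneumonitis and bronchopulmonary hemorrhage as separate terms. A reader might infer that pneumothorax is merged with radiation injury; it is not. That stands, and it limits the problem to shared terms.

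A reader might also infer that implant-period events in phase II are lost. The documents do not support this. Section 10.0, on treatment, opens with beacon placement, and the phase II list makes placement step 1 of Calypso-guided SABR. Treatment therefore most naturally includes the implant, and objective 2 covers it without naming it.

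Nor do the documents support the inference that implant harm is beyond estimation. The assessments are scheduled for all 28; only the summary is missing. Radiation sparing does not depend on this table either, because the PTV and organ-at-risk metrics measure it.

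There are other safeguards. SAEs are reported regardless of causality, and the monitoring committee reviews secondary endpoints once the fourteenth patient has completed the first follow-up visit. Total toxicity of the strategy is itself a reasonable planning input. All this is fair, but none of it restores the timing that the maximum discards or produces the acute and late split.

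The COPD exacerbation risk of up to 11% in section 11.0 is not used here. It comes from 9 patients with non-Calypso markers, and the same paragraph cites larger series with none.

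**Conclusion.** The concern holds in a limited form. The plan collects implant-period toxicity in all 28 patients but does not specify a summary of it. For shared terms its stated rule lets a later, higher grade replace an implant-period one. The same rule does not deliver the acute and late quantification that phase II objective 2 calls for. The named implant objective and the safety hypothesis rest on two patients, where zero events would still leave an upper limit of 84.2%, against 12.3% in 28.

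This assumes that all 28 planned patients are implanted and assessed at 4DCT, and that the listed terms can arise from either procedure. It does not show that the trial could measure the added harm or net benefit of the Calypso strategy. A single arm gives an absolute rate for the implant period under any windowing. The change is worth making because it is cheap; the primary endpoint is unaffected.

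**What to change.** Extend the implant-toxicity objective in section 6.0 to all implanted patients in both phases, and base the placement-safety statement on them. In section 13.0, tabulate maximum grade by adverse effect in three windows, and keep the overall maximum beside them:

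1. Implantation to before the first fraction: new or worsened grade from baseline at the 4DCT visit, plus any dated AE or SAE before fraction 1. Report as n/28 with an exact 95% interval.
2. First fraction through the 2-month visit.
3. After the 2-month visit.

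The 2-month cut is a convention, because the plan defines no boundary between acute and late; it is the first follow-up visit in section 12.0.

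The cost is wording in two sections and a few table columns, with no new visit. If onset dates of non-serious events are not already recorded, window 1 should rest on the 4DCT grade and dated SAEs, or an onset-date field should be added.

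Three limits should be stated with the results. There is no CTCAE visit at bronchoscopy itself. The fraction 1 assessment is not stated to precede the beam, so it should not define the end of window 1. Windows are not attribution: a beacon event after fraction 1, such as late infection or migration, falls in a later window.

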14.0 Biobanking of Serum & Urine

In parallel to this study, patients will be offered voluntary participation in the Manitoba Tumor Bank (operating under auspices of the Manitoba Tumor Bank's Informed Consent Form). Blood and urine specimens from consenting volunteers will be collected at baseline, on the last day of SABR, at 6 months, and 1 year of follow up. This will allow for correlative biomarker studies to be performed in the future.

15.0 Ethical Considerations

This study will be carried out with the written approval of the biomedical research ethics board of the University of Manitoba. All patient care for this study will be in accordance with the principles of human medical research outline in the Declaration of Helsinki as adopted by the World Medical Association.

This study will be conducted in accordance with the International Conference on Harmonization (ICH) for Good Clinical Practice (GCP) and the appropriate regulatory requirements. The investigators will be familiar with the appropriate study treatments as described in the protocol. Essential clinical documents will be maintained to demonstrate the validity of the study and the integrity of the data collected.

16.0 Protocol Treatment Discontinuation

Patients may discontinue protocol treatment in the following circumstances:

- 1) Unacceptable toxicity (defined as any grade 3 or higher NCI CTCAE 4.0 acute toxicity relating to either the radiotherapy or the study drug); or
- 2) The development of an intercurrent illness that would preclude the continuation of the study treatment; or
- 3) Development of an intercurrent illness that would preclude further clinical assessments; or
- 4) Request by the patient; or
- 5) Completion of study therapy and follow-up as per section 12; or
- 6) Cancer recurrence or progression (based on any combination of imaging, biochemical or clinical findings).

Patient management following stoppage of protocol treatment is to be reviewed by the Principal Investigators of the study ([name] and [name]). This will allow the Principal Investigators to provide recommendations on the schedule and duration of additional follow-up, depending on the value of additional follow-up, patient convenience, trial safety, etc.

17.0 Serious Adverse Event Reporting

A serious adverse event (SAE) is any adverse event, regardless of causality that:

- Results in death.
- Is life-threatening. (When a patient is at immediate risk of death from a reaction as it occurred, i.e., it does not include a reaction which hypothetically might have caused death had it occurred in a more severe form.
- Requires in-patient hospitalisation or prolongation of existing hospitalisation. Hospitalisation admissions and/or surgical operations scheduled to occur during the study period, but planned prior to study entry are not considered AEs if the illness or disease existed before the patient was enrolled in the trial, provided that it did not deteriorate in an unexpected manner during the trial (e.g., surgery performed earlier than planned).
- Results in persistent or significant disability/incapacity. Disability is defined as a substantial disruption of a persons' ability to conduct normal life functions.
- Is a congenital anomaly/birth defect.
- Is an important medical event. An important medical event is an event that may not result in death, be life-threatening, or require hospitalization but may be considered an SAE when, based upon appropriate medical judgment, it may jeopardize the patient or subject and may require medical or surgical intervention to prevent one of the outcomes listed in the definitions for SAEs. Examples of such medical events include allergic bronchospasm requiring intensive treatment in an emergency room or at home, blood dyscrasias or convulsions that do not result in inpatient hospitalization, or the development of drug dependency or drug abuse.

Clarification should be made between the terms "serious" and "severe" since they are not synonymous. The term "severe" is often used to describe the intensity (severity) of a specific event (as in mild, moderate, or severe myocardial infarction); the event itself, however, may be of relatively minor medical significance (such as a severe headache). This is not the same as "serious" which is based on patient/event outcome or action criteria described above and are usually associated with events that pose a threat to a patient's life or functioning. A severe adverse event does not necessarily need to be considered serious. For example, persistent nausea of several hours duration may be considered severe nausea but not an SAE. On the other hand, a stroke resulting in only a minor degree of disability may be considered mild, but would be defined as an SAE based on the above noted criteria.

Serious Adverse Event requires reporting with completion of the SAE report. Fax the SAE report within 24 hours of the investigator knowledge or designee knowledge of the event to the attention of: [name] and [name] to [contact] (fax). Accrual may be stopped immediately as indicated upon review and confirmation of the SAE by the co-PIs in liaison with the investigator/ Research Ethics Board. This trial will conform to the monitoring requirements of Biomedical Research Ethics Board of the University of Manitoba.

